### **5.6.4. Treatment-emergent Adverse Events**

An AE is considered treatment-emergent if its start date is on or after the date of first dose of study treatment in Study 205 or if the AE is on-going from the prior study. If the AE start date is missing and the AE stop date is after the start date of the first dose of study treatment (or the AE is ongoing) then the AE will be considered treatment emergent. If either or both times are missing, then dates alone will be compared. See Section 5.7.2 for incomplete dates or times.

AEs occurring 30 days after the last dose will be considered as TEAEs. All AEs that occurred more than 30 days after the last dose of study treatment will be excluded from the tables and listings. AEs that occurred during the dose tapering period will be included in the tables and listings. Adverse events that rolled over from the parent study are excluded from the tables but will be included in the listings.

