Male subjects with a female partner of childbearing potential, unless vasectomized, must use condoms (with spermicide, where available) for the purposes of contraception throughout the study and for a duration of 90 days after the last dose of study drug. It is not known if BCX9930 or BCX13559, the major metabolite of BCX9930, are present in human semen. Therefore, subjects with a pregnant female partner must use condoms to avoid potential exposure of the partner and fetus in utero through semen.

Male subjects must abstain from sperm donation throughout the study and for a duration of 90 days after last dose of study drug.

Abstinence as a contraceptive method will not be an option for subjects regardless of lifestyle or sexual activity.

Per European Clinical Trials Facilitation and Coordination Group guidance, contraception and pregnancy testing requirements must remain in place through the end of relevant systemic exposure ([CTFG 2020](#)). Based on data generated in healthy subjects in Study 101, the geometric mean half-life of BCX9930 was  $\leq 17.35$  hours (suggesting that 5 half-lives are elapsed within approximately 3.6 days). Further, the human mass balance study (Study 102) identified BCX13559 (an acyl glucuronide) as the only major metabolite of BCX9930. Clearance of BCX13559 was determined to be formation-rate limited. Study 102 also showed all subjects achieved  $> 90\%$  recovery of the administered radioactive dose within 12 days (single dose). Together, these findings suggest that the end of relevant systemic exposure for BCX9930 and BCX13559 occurs well before the ET or EOS visit performed approximately 3 weeks after the last dose of BCX9930.

Methods of contraception, as applicable, for both male and female participants should be documented in the source documentation. Investigators will also review each subject's continued use of contraception at periodic intervals to ensure compliance with the protocol contraception requirements, including reminding subjects about the need to renew their contraception.

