### 12.4. Method, Frequency, and Time Period for Detecting Adverse Events and Reporting Serious Adverse Events

Reports of all AEs and SAEs, regardless of investigator attribution, are to be collected from the time of enrollment through to the last study visit (ie, through the post-treatment follow-up

visit). If AEs/SAEs occur after the subject has signed the informed consent form (ICF) for Study 205 but while the subject is still enrolled in the prior study, the AEs/SAEs will be collected according to the procedures specified in the prior study protocol. All AEs and SAEs are to be reported on the AE eCRF.

AEs should be documented on the eCRFs as investigators become aware of them. AEs are to be followed until the event resolves. If an event is ongoing at the last follow-up visit, Grade 1 and Grade 2 events do not need to be followed if the event is deemed unlikely to be related or not related to study drug/IMP (see Section 12.2 for AE grading). For all Grade 3 and Grade 4 events or events deemed possibly, probably, or definitely related to use of study drug/IMP, the event should be followed until the AE is resolved or the subject is in a clinically stable condition with regard to the AE.

The investigator shall report all SAEs immediately and no later than 24 hours of their knowledge of the event to the sponsor by communicating with the medical monitor (phone or email) and by entering the event into the AE eCRF and by completion of the SAE eCRF. The SAE eCRF is an additional form to the AE eCRF that provides important details on the SAE. The investigator should follow all unresolved SAEs observed during the study until they are resolved, or are judged medically stable, or are otherwise medically explained.

The investigator should attempt, if possible, to establish a diagnosis based on the presenting signs and symptoms. In such cases, the diagnosis should be documented as the AE and not the individual sign/symptom. If a clear diagnosis cannot be established, each sign and symptom must be recorded individually. Once a diagnosis is made during evaluation or treatment, the investigator will update the AE record with this diagnosis and delete the previously reported signs and symptoms. The rapid reporting of SAEs ensures that the sponsor shall have the necessary information to continuously assess the benefit-risk profile of the study drug in clinical studies.

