### **12.5.3. Risk of Hemolysis After Missed Doses, Treatment Interruption, or Permanent Discontinuation**

Investigators should remind subjects of the potential risk of hemolysis following missed doses (particularly multiple consecutive missed doses) and treatment interruption, and the definite risk after permanent discontinuation of BCX9930. By inhibiting the AP of complement, BCX9930 may improve Hb levels and increase circulating RBC clone size by reducing the hemolysis of PNH RBCs. Missed doses and treatment interruption of BCX9930 may lead to hemolysis. Subjects are at risk of severe hemolysis when BCX9930 is permanently discontinued. Based on available data regarding the PK and PD of BCX9930, severe hemolysis, if it occurs, would be expected to present within days after discontinuation of therapy.

Monitoring for hemolysis should be performed based on the medical judgement of the investigator. However, when subjects permanently discontinue BCX9930 at any time during the study, the following recommendations are made:

- If the subject is asymptomatic, it is recommended that contact with the subject be maintained on a daily basis for a minimum of 7 days. Contact may be conducted by telephone, email, or other means, including in person, if preferred. When any sign or symptom of hemolysis occurs, the subject should be promptly evaluated. Additional monitoring following the first contact after permanent discontinuation should be guided by the medical judgement of the investigator.

- For subjects who are already symptomatic when treatment is discontinued, whether the subject should be assessed in person or can be followed with daily contact will be based on the investigator's medical judgement taking into account the severity of the reported signs or symptoms and/or any reported worsening of the signs or symptoms. When possible, subjects should return to the investigative center; however, when this is not possible, arrangements may be made for the subject to be assessed by his or her local hematologist and a local laboratory used for clinical laboratory testing. When hemolysis occurs after the permanent discontinuation of BCX9930, treatment should be provided according to the judgement of the investigator.

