## 13. STATISTICS

### 13.1. Sample Size Considerations

No sample size calculations were conducted for this open-label, long-term safety study. Up to 30 subjects may be enrolled in this study, to allow continued access to BCX9930 following a subject's participation in another BCX9930 study.

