**Number of Subjects (planned):**

Up to 30 subjects are planned.

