### 7.1. Efficacy Analysis of Hemoglobin

Descriptive statistics for the observed values and changes from baseline in hemoglobin in the safety population will be presented for all scheduled visits during the treatment period. Values recorded within 14 days after the subject received a pRBC or whole blood transfusion will be excluded from the summary statistics. Unscheduled visits will be presented in the data listings but not summarized in the table.

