### **8.1. Overall Summary of Treatment-emergent Adverse Events**

The overall summary of TEAEs table for all subjects in the safety population will summarize the number and percentage of subjects that report at least 1 TEAE, have a treatment-related TEAE, have a TEAE leading to treatment withdrawal, have a serious TEAE requiring concomitant medication, have a severe (Grade 3) or life-threatening (Grade 4) TEAE, have a serious TEAE, have a TEAE leading to study discontinuation, and have a TEAE leading to death. In addition to summarizing the number and percentage of subjects that have at least 1 of these events, the table will also summarize the total number and percentage for each of these events. Results will be summarized for the BCX9930 400 mg BID, dose taper and Total. The percentages for number of subjects will use the safety population sample size as the denominator; the percentages for the number of events will use the total number of TEAEs as the denominator.

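### The TEAE tables count AEs up to 30 days after last dose but have no post-treatment column and no next-therapy flag, so they cannot separate on-drug events from those after stopping or switching

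*SAP*

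**What the plan says.** **Window.** SAP 5.6.4: "AEs occurring 30 days after the last dose will be considered as TEAEs". The next sentence removes only AEs more than 30 days after last dose, so I read the rule as covering the whole of days 1 to 30. AEs during the taper are kept. The start of another PNH therapy is not mentioned.

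**Columns.** SAP 8.1: "Results will be summarized for the BCX9930 400 mg BID, dose taper and Total". SAP 8.2.1, 8.2.2.1 and 8.2.2.2 repeat this. The renal and hepatic tables (8.2.2.3, 8.2.2.4) name no columns. The exposure table (6.4) uses the same three columns and counts days of exposure.

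**Stopping.** Treatment is capped at 96 weeks and ends sooner if another PNH therapy becomes available (Protocol 5.2, 7.1, 7.4.1). Protocol 12.5.3: "Subjects are at risk of severe hemolysis when BCX9930 is permanently discontinued". The same section calls the hemolysis risk after permanent discontinuation definite and expects severe cases to show within days.

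**Collection.** Under Protocol 12.4, AEs are "collected from the time of enrollment through to the last study visit". That visit is EOS/ET, 3 weeks ± 3 days after last dose (Protocol 10.1).

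**Size of study.** SAP synopsis: "Up to 30 subjects are planned". Protocol 13.1: "No sample size calculations were conducted for this open-label, long-term safety study".

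**The concern.** The second objective (Protocol 6.1, SAP 2.1) is safety in subjects who are still taking BCX9930. Three kinds of event fall inside the TEAE definition: those on drug, those caused by the disease returning once the drug is withdrawn, and those arising on the next PNH therapy. They answer different questions. The taper has its own column, but the taper is still dosing, so no column describes a subject who has stopped.

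Two programmers following the SAP could place the same post-last-dose hemolysis differently: one under the last regimen taken, the other only in Total. Neither choice would breach the SAP, and a reader of the table could not tell which had been made.

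The mixing could extend to the organ-specific tables. Protocol 12.5.2 notes that creatinine can rise with hemolysis, and 12.5.1 allows for hemolysis-driven AST and bilirubin rises. If such changes after stopping are recorded as AEs, they could appear in the renal and hepatic TEAE tables with nothing to show that the subject was off drug.

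**Working it through.** **1. The plan's own figure.** Protocol 11.2.1 gives a half-life of at most 17.35 h, "suggesting that 5 half-lives are elapsed within approximately 3.6 days".

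- 5 × 17.35 h = 86.75 h; 86.75 / 24 = 3.61 days. The stated figure reproduces.
- Share of the 30-day window beyond that: (30 − 3.61) / 30 = 88%.
- Conservative bound, using the 12 days within which the same section reports over 90% recovery of radioactivity: (30 − 12) / 30 = 60%.
- For the time to EOS/ET at day 21: (21 − 3.61) / 21 = 83%, or (21 − 12) / 21 = 43%.

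On either bound, most of the 30-day window lies after relevant exposure. The half-life comes from healthy subjects and the recovery figure from a single dose. I use them only to show that this period is not on-drug time, not to set a boundary.

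**2. Where an AE goes, by state at onset.**

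| Onset | TEAE under 5.6.4? | Column under 8.1 to 8.2.2.2 |
|---|---|---|
| On 400 mg BID | Yes | 400 mg BID and Total |
| During taper | Yes | Dose taper and Total |
| Days 1 to 30 after last dose | Yes | Not stated |
| Days 1 to 30, after another PNH therapy starts | Yes | Not stated, and not marked |

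**3. How much of the window is observed.** EOS/ET falls at 21 ± 3 = day 18 to 24. Days without routine collection: 30 − 24 = 6 to 30 − 18 = 12, which is 20% to 40% of the 30 days.

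**4. Weight of the post-dose period.** Its share of one subject's TEAE observation time after w weeks on drug, with EOS/ET at day 21, is 21 / (7w + 21).

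| Weeks on drug | Share |
|---|---|
| 8 | 21 / 77 = 27% |
| 24 | 21 / 189 = 11% |
| 48 | 21 / 357 = 5.9% |
| 96 | 21 / 693 = 3.0% |

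These are shares of time, not of events. If hemolysis clusters just after stopping, the share of events could be larger.

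**5. Effect on a printed percentage (assumed rates only).** With 30 subjects, each one is 1 / 30 = 3.3 percentage points. Let q be the on-drug risk of a given TEAE and p the risk after stopping, assumed independent. A column holding both reads 1 − (1 − q)(1 − p). With q assumed at 10%:

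- p = 10%: 19%
- p = 20%: 28%
- p = 40%: 46%

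A split table would still show 10% on drug. Total is affected in every case. The 400 mg BID column is affected only if post-dose events are placed there.

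**The case against.** **Treatment-emergent status is about timing, not cause.** True. A 30-day tail is not wrong in itself, and it keeps withdrawal hemolysis in the tables. A reader might infer that the withdrawal risk is hidden. The documents do not support that, because these events are tabulated and listed.

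**On-drug rates are not shown to be inflated.** A reader might also infer that post-dose events are credited to 400 mg BID. The SAP makes no such assignment, and they may sit only in Total. What stands is the missing rule.

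**Causality is handled separately, and listings exist.** The overall table has a treatment-related row, and under Protocol 12.3 an event explained by another therapy can be judged unrelated. Listings of AEs, exposure, concomitant medications, transfusions and Hb/LDH allow case-by-case reconstruction in at most 30 subjects. This limits the harm. But the related row rests on investigator judgement rather than timing, and no planned table shows the split.

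**Hb and LDH.** SAP 7.1 summaries "will be presented for all scheduled visits during the treatment period", which leaves out EOS/ET because Protocol Table 2 puts that visit in a separate column; SAP 7.2.1 does the same for LDH. It is tempting to call this a second defect. These are efficacy tables, on-treatment visits are a coherent scope, and SAP 5.6.7 has all post-baseline values listed. A visit 3 weeks after stopping would also describe hemolysis expected within days poorly. An EOS/ET row is a preference.

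**Sharper cut-offs.** Starting the off-drug period at 3.6 days would count the earliest rebound as on drug. Ending the window at EOS/ET would drop later events that are reported and leave it undefined for subjects with no such visit. Neither is warranted. A cap longer than routine collection does no harm if it is disclosed.

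**Conclusion.** The concern holds as a gap in the column rule and in next-therapy identification. As written, the main TEAE tables cannot separate safety on BCX9930 from events after withdrawal or on a successor therapy: the latter are either mixed into an on-drug column or visible only within Total.

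The size is unknown, because the documents give no post-stop event rates and no switch frequency or timing. By time alone, the post-dose period is small for a subject treated for 96 weeks (3%) and substantial for one who leaves at 8 weeks (27%), assuming EOS/ET at day 21. The percentages under assumed risks show the mechanism and are not estimates.

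A related mismatch is that the Total TEAE column draws on more time than the Total exposure column, which counts dosed days only.

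This is a descriptive, abbreviated report with full listings, so the gap does not invalidate it. It should be closed because doing so costs very little.

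**What to change.** - **SAP 5.6.4.** Keep the 30-day window. Assign each TEAE by state at onset: 400 mg BID, taper, or post-treatment. Post-treatment starts the day after the last dose, taper doses included.
- **SAP 8.1 to 8.2.2.4.** Add a post-treatment column to the TEAE tables, and state the columns of the renal and hepatic tables. Keep the safety-population denominator, and print the number of subjects with any post-treatment follow-up.
- **Next therapy.** Flag TEAEs with onset on or after the first dose of another PNH therapy, using the concomitant-medication dates recorded through EOS/ET.
- **Partial dates.** Add a rule for period assignment. SAP 5.7.1, applied to AEs by 5.7.2, can move a partly missing start date to the first dose of study drug, which could shift a post-treatment AE or a successor therapy into the on-drug period.
- **Footnote.** State that routine AE collection ends at EOS/ET, about day 18 to 24, so the rest of the 30 days is not systematically observed.
- **Optional.** Add an EOS/ET row, labelled off drug, to Tables 14.2.1.1 and 14.2.2.3.

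The cost is SAP wording and programming. No new data, visits or changes to clinical management are needed. The downside is one more column with small counts.

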### **12.1.2. Serious Adverse Event**

A serious adverse event (SAE) is an AE/reaction that results in any of the following outcomes:

- Death
- Is life-threatening (subject is at immediate risk of death at the time of the event; it does not refer to an event that hypothetically might have caused death if it were more severe)
- Requires subject hospitalization (formal admission to a hospital for medical reasons) or prolongation of existing hospitalization
- Results in persistent or significant disability/incapacity (ie, there is a substantial disruption of a person’s ability to carry out normal life functions)
- Is a congenital anomaly/birth defect

Important medical events that may not result in death, are not life-threatening, or do not require hospitalization may be considered SAEs when, based upon appropriate medical judgment, they may jeopardize the subject’s health or may require medical or surgical intervention to prevent one of the outcomes listed in this definition. Examples of such events

may include allergic bronchospasm requiring intensive treatment in an emergency room or at home, blood dyscrasias, or convulsions that do not result in subject hospitalization.

In addition, the sponsor considers any abortions (elective or spontaneous), fetal demise, and still birth to be SAEs for reporting purposes (see Section 12.4.2).

Some hospitalization scenarios, as outlined in Section 12.1.1, do not require reporting as SAEs.

Overdose will be considered an SAE only if any of the seriousness criteria are met. Any clinical complication in association with the overdose should be reported as an AE or SAE (as applicable) along with the overdose (see Section 12.6). Details of signs or symptoms, clinical management, and outcome should be reported, if available. Overdose without associated signs or symptoms should not be recorded as AEs but should be recorded as protocol deviations.

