#### **12.4.1. Serious Adverse Events and Suspected Unexpected Serious Adverse Reactions**

The investigator must report all SAEs immediately and in no case later than within 24 hours of their knowledge of the event. Investigators should adhere to their country or region requirements for the reporting timeframe, which may not allow any delay. SAEs should be reported to the sponsor medical monitor and via the AE and SAE eCRFs. The SAE eCRF is an additional form to the AE eCRF that provides important details on the SAE. All additional follow-up evaluations of the SAE must be reported to BioCryst or its designee as soon as they are available by amending these eCRFs.

In the event the eCRF system is not functioning, the reporting of an SAE must not be delayed. Sites will have SAE report forms (electronic Word document) that can be completed and emailed to the below recipient. As soon as the eCRF system is functioning, that particular SAE must be entered into the AE eCRF. The eCRF system automatically sends SAE notifications to the following email address: [[contact]](mailto:[contact]).

Immediate reporting should allow BioCryst to take the appropriate measures to address potential new risks in a clinical study. Therefore, the initial report should be submitted by the investigator within a very short period of time and under no circumstances should this period exceed 24 hours following awareness of the SAE.

The follow-up report should allow BioCryst to determine whether the SAE requires a reassessment of the benefit-risk profile of the study drug/IMP in clinical study, if the relevant information was not already available and provided in the initial report.

Country-specific rules and requirements for safety management will be described in the Safety Management Plan prepared for this study.

Investigators or designees at each site are responsible for retaining copies of all suspected unexpected serious adverse reaction (SUSAR) reports (initial and follow-up) and other safety information (eg, revised IB) in the investigator site files.

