**CCI**

**CCI**

#### **12.4.2. Pregnancy**

Any female subject who becomes pregnant during the course of the study should have BCX9930 discontinued immediately and must be followed through the end of the pregnancy. While pregnancy is not considered an AE, all cases of fetal drug exposure via the parent as a study participant (including partners of study participants) are to be reported immediately to BioCryst or its designee. Consent from study partners who become pregnant will be obtained prior to reporting any details of the pregnancy. Information related to the pregnancy must be given on a “Pregnancy Notification and Outcome” form that will be provided by the sponsor or its designee so that the pregnancy may be followed, and an outcome determined. Any AEs or SAEs experienced by a pregnant subject are to be reported as directed in Section 12.4.1.

Any complications reported in a subject’s pregnant partner should be reported on the Pregnancy Notification and Outcome form. All pregnancies must be followed to outcome, which occurs when an infant is delivered (live or still born), there is fetal demise, or there is an abortion (spontaneous or induced). Abortion (spontaneous or induced), fetal demise, and still birth, along with congenital abnormalities in the newborn, should be reported as separate SAEs.

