#### 13.3.2. General Considerations for Data Analysis

In general, descriptive summaries will include the sample size (n), mean, standard deviation (SD) and/or standard error (SE), median, minimum, and maximum for continuous variables and n and percentage for categorical variables. Data will be summarized by prior study and overall. Summaries will be presented by study visit where appropriate (eg, laboratory data) until subjects complete or withdraw from the study. No missing value imputation will be done. No statistical testing is anticipated as there are no a priori hypotheses stated for this study.

All individual subject data will be listed as measured. All statistical summaries and analyses will be performed using SAS® software (SAS Institute, Cary, North Carolina, USA), using version 9.4 or higher.

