## **8. SAFETY AND TOLERABILITY**

All study safety data to support the aCSR will be presented in data listings.

AEs will be assessed and recorded from the time of signing of the informed consent through the appropriate follow-up period. AEs will be mapped to MedDRA version 24.0 preferred term (PT) and system organ class (SOC). Relationship to study treatment will be assessed as not related, unlikely related, possibly related, probably related, or definitely related. AEs will be graded according to the CTCAE scales (Version 5.0, 27 November 2017). AEs not covered by CTCAE criteria will be assessed for severity as mild, moderate, severe, or life-threatening, corresponding to toxicity Grades 1 through 4.

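### The SAP's 30-day cut removes late adverse events from the listings as well as the tables, so a female subject's late pregnancy-outcome SAE would appear in no planned display

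*SAP*

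**What the plan says.** SAP 5.6.4 counts AEs up to 30 days after the last dose as treatment-emergent and then adds: "All AEs that occurred more than 30 days after the last dose of study treatment will be excluded from the tables and listings". Two sentences later it treats another group differently: "Adverse events that rolled over from the parent study are excluded from the tables but will be included in the listings".

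The protocol has a specific rule for pregnancy. Section 12.4.2 says that a female subject who becomes pregnant "should have BCX9930 discontinued immediately and must be followed through the end of the pregnancy". It also says that abortion, fetal demise and still birth, "along with congenital abnormalities in the newborn, should be reported as separate SAEs". Section 12.1.2 agrees: "the sponsor considers any abortions (elective or spontaneous), fetal demise, and still birth to be SAEs for reporting purposes". For a pregnant subject's own AEs and SAEs, 12.4.2 refers to Section 12.4.1, where "SAEs should be reported to the sponsor medical monitor and via the AE and SAE eCRFs".

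On listings in general, Protocol 13.3.2 says "All individual subject data will be listed as measured", and SAP 8 says "All study safety data to support the aCSR will be presented in data listings". SAP 9.1.2 plans one SAE listing, 16.2.7.2. SAP 9.1.1 and 9.1.2 contain no pregnancy display and no separate display of deaths or post-treatment SAEs.

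**The concern.** A time cut on treatment-emergent events is normal for incidence tables. Applying it to the listings is different, because a listing is the only place where a single late event can be seen. Here the cut removes a type of SAE that the protocol specifically requires to be followed and reported.

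These are also the outcomes that bear on a risk the protocol names. Section 5.3 describes a potential teratogenic risk from a mouse study, at an exposure margin below 1. It also says that no such risk was found in rats or rabbits and that no malformations were reported among 3 first-trimester exposures in clinical studies. With so few exposed pregnancies, each outcome counts individually. If a female subject became pregnant in Study 205, the abbreviated report's listings would show an early loss but could omit a still birth, a later fetal demise or a congenital abnormality.

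**Working it through.** The plan gives no figure to reproduce on this point. The check compares the passages and then does date arithmetic.

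**1. Does the cut reach the listings?** Yes. The sentence covers all AEs and names both display types. The rolled-over-event sentence in the same section removes events from tables but keeps them in listings. The SAP separates the two when it means to, so the 30-day rule cannot be read as tables only.

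**2. Would the records exist?** Routine AE collection ends at the last study visit (Protocol 12.4). That visit is 21 ± 3 days after the last dose (Protocol 10.1):

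- 21 − 3 = day 18; 21 + 3 = day 24
- distance to the cut: 30 − 24 = 6 days to 30 − 18 = 12 days

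The cut therefore lies 6 to 12 days beyond routine collection and removes little routine data. It acts mainly on SAEs learned of later. Pregnancy outcomes are the ones the protocol requires to be pursued (12.4.2), and 12.4.1 sends SAEs to the eCRFs.

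**3. When do the outcomes fall?** Days from last dose to outcome = 7 × (gestational week at outcome − gestational week at last dose). Days past the cut = that result − 30. The week at last dose is assumed to be 4 to 12; the documents do not give it.

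| | Last dose at week 4 | Last dose at week 12 |
|---|---|---|
| Cut falls at week | 4 + 30/7 = 8.3 | 12 + 30/7 = 16.3 |
| Outcome at week 20, days after last dose | 7 × 16 = 112 | 7 × 8 = 56 |
| Days past the cut | 112 − 30 = 82 | 56 − 30 = 26 |
| Outcome at week 40, days after last dose | 7 × 36 = 252 | 7 × 28 = 196 |
| Days past the cut | 252 − 30 = 222 | 196 − 30 = 166 |

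Across this range every outcome at week 20 or later is excluded. Losses before the cut (week 8.3 to 16.3) are kept.

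**4. Would another display show them?** The AE displays are Tables 14.3.1.1 to 14.3.2.5 and Listings 16.2.7.1 to 16.2.7.4, and all fall under 5.6.4. The disposition table and listing could show pregnancy as a reason for stopping, but not its outcome.

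**5. Is the exclusion declared as a change?** No. SAP 9 restricts output to the variables relevant to the abbreviated report. It does not mention leaving out SAE records, and SAEs are evidently relevant because they have their own listing.

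**The case against.** The case against has several parts.

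- **Listing title.** Listing 16.2.7.2 is not titled as treatment-emergent, unlike the other three AE listings, and the cut sits under a treatment-emergent heading. A programmer might therefore include a late SAE. That is possible, but the sentence covers all AEs and the listings without qualification. At best there are two readings to reconcile.
- **Scope of the general statements.** SAP 8 is limited to data supporting the abbreviated report, and SAP 9 announces a general narrowing. The first point has some weight. The second concerns variables, not records, so the conflict with Protocol 13.3.2 remains.
- **Database lock.** SAP 4.2 allows analysis once all subjects complete or discontinue, and nothing holds the lock for a pregnancy still in progress. For a late pregnancy, the lock itself could keep the outcome out. This stands. It limits how often the SAP rule decides the matter but does not justify the rule.
- **Newborn abnormalities.** The protocol requires an SAE but does not say whose record holds it or what onset date it carries. This also stands, and it makes the congenital-abnormality case less certain than fetal demise or still birth.
- **Rarity.** There are up to 30 subjects of both sexes, women of childbearing potential must use highly effective contraception, and development has ended. The consequence is a possible missing row in an abbreviated report. This is true and sets the scale of the point.
- **Additional listings.** SAP 9.1 lets supporting listings be added without revision. That is permission, not a plan.

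**Conclusion.** The concern holds. As written, SAP 5.6.4 would remove from every planned display a pregnancy-outcome SAE in a female subject with onset more than 30 days after her last dose. For dosing stopped at gestational week 4 to 12, that means every outcome at week 20 or later, by 26 to 82 days at week 20 and by 166 to 222 days at week 40. These figures rest on the assumed stopping week and on the SAE being in the database at lock.

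The effect is confined to listing rows. Not affected are:

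- losses within 30 days of the last dose;
- events with onset by day 30 whose fatal outcome or report comes later;
- eCRF collection, follow-up and expedited reporting;
- every tabulated percentage.

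Partner pregnancies are outside this point, since their complications go on the separate pregnancy form. The case is hypothetical, but the rule should be corrected because it conflicts with the protocol's commitment on listings and the correction costs almost nothing.

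**What to change.** Amend SAP 5.6.4 so that the 30-day cut applies to the treatment-emergent summary tables only. State that all AEs and SAEs in the database are listed whatever their onset, with days from last dose and a flag for onset beyond 30 days. At minimum, apply this to all SAEs in Listing 16.2.7.2 and name pregnancy outcomes as included. The same section already handles rolled-over events this way.

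The cost is one sentence in 5.6.4 and a flag column in Listings 16.2.7.1 and 16.2.7.2. If 16.2.7.1 is widened, its title should change too, which SAP 9.1 allows without a revision. No new data are needed. The change lists what is in the database; it does not settle how a pregnancy still in progress at lock is handled.
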